Phenotypic Outcomes (AIM 1) and Biomarker DNA Age (AIM 2): We hypothesize that the VTEL high-intensity circuit exercise intervention will increase cardiorespiratory fitness and decrease sarcopenia and frailty (AIM 1) and decrease DNA Age (AIM 2). ANOVA models will be used with dependent variables of cardiorespiratory fitness (VO₂peak, 2-minute step test) and DNA Age (years). Logistic or multinomial models will be used with dependent variables of sarcopenia (present/not present) and frailty (robust/pre-frail/frail). Secondary analyses will be performed that use the individual components of composite outcome as their own dependent variable (e.g., lean mass and strength from sarcopenia). ANCOVA will be used to test for between group difference by time (pre/post exercise). Baseline performance and demographic and clinical characteristics will be included in models to assess and adjust for known potential confounding factors based on our experience with older HIV+ adults. We do not expect significant variability or effect from HIV-related factors (e.g., antiretroviral therapy, viral load) since we will use our previous established eligibility criteria. We do not anticipate needing to adjust for sex or race since each individual will function as their own control. Nutritional analyses of macro and micronutrients will be performed to measure any change during the study, and if present, will be tested for within group and between group effects. A similar approach will be applied to smoking exposure, which will be quantitated at baseline and follow-up testing. Treatment fidelity will be measured as percent of AEX time at target heart and entered in ANOVA models. For future planning, feasibility analyses will include calculation of rates for enrollment, retention, and attendance overall and by HIV group. Aggregate data will be collected on adverse events and reasons for lost to follow-up.

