Analyses will include participants who drop out before completion of the 12-week intervention period by way of multiple imputation. This intention to treat approach will investigate factors that may affect compliance and difficulty with exercise training, including soreness and medical comorbidity. If the pattern of missing data is missing completely at random, or simply at random, our multiple imputation should eliminate bias due to loss to follow-up. Because the participants will be recruited from clinic-based VA cohorts, we will be able to obtain clinical data from participants who drop out of the study, but remain in clinical care, to determine if drop-out was related to medical conditions that may influence outcomes. Thus, we will be able to estimate bias introduced by loss to follow-up. If there is sufficient information, we may be able to model the drop-out process and adjust our analyses for loss to follow-up even if the missing data pattern is non-ignorable. If 36 training sessions cannot be completed in 12 weeks, then total training time will be tracked, and incorporated into the data analysis.

DNA Methylation (AIM 3): We will examine the change of methylation levels after 12 weeks for each candidate marker using ANOVA models. To examine epigenetic association with each outcome, we will fit the linear regression model as follows: where Y_i is the quantitative outcome measurement, Z_i is the vector of covariates including age, race, smoking status and leukocyte proportions, and E_i is the candidate epigenetic marker. ANCOVA will be used to test for between group difference by time (pre/post exercise). The candidate epigenetic markers will involve individual CpG sites previously identified and discussed in detail section D4c. We will extend this linear regression model to account for batch/chip effects and

longitudinal measures using a linear mixed model. We will adjust the significance threshold for multiple testing using Bonferroni correction ($p < 0.05 / \text{number of tests}$).

Sample Size Estimates:

AIM 1. Paired t-test was used to test for a mean change given a range of correlation between pre and post values with assumptions of $\alpha = 0.05$ and 80% power. (Mean (SD) values for the VO_2peak are from our current high-intensity AEX + RT trial in HIV+ Veterans (Table 3). Data for 2-minute step test are from our VTEL Gerofit exercise program (C3). Values for chair stands are results from a 10-week RT in older men.⁴⁶ We will have adequate

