3 STUDY METHODS

3.1 Study Design

This study is a multi-site exercise intervention for Veterans receiving care at the Atlanta and Baltimore VAMCs that will randomize approximately 80 participants (40 per site) at these VAMCs, herein referred as enrollment sites. The intervention is 12-weeks of high-intensity functional circuit exercise performed 3 times weekly in a supervised group setting. Exercise training will be led by an exercise physiologist at the Salem VAMC (coordinating site) and broadcast to the enrollment sites. HIV-infected Veterans 50 years of age and older will be enrolled at the Atlanta and Baltimore VAMCs. Eligible participants will be randomized to exercise training (N=40) or control (N=40) groups. All participants will undergo baseline testing and follow up testing after 12 weeks at their respective enrollment site. Participants in the Control Group will be instructed to maintain their baseline sedentary lifestyle (as defined in eligibility criteria) during the 12-week intervention period. After follow-up testing is complete, participants in the control group will have the option of completing 12-week exercise training (delayed entry exercise) which will be a combined home and center-based exercise program. Pre-post exercise testing will be conducted in these participants to gauge individual progress and provide individual feedback that is a benefit of study participation, but these results will not be part of the randomized trial analyses.

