AEX, aerobic exercise; RT, resistance training

progress and any issues will be discussed on the monthly VTEL conferences with Drs. [name] (Salem), [name] (Baltimore), and [name] (Atlanta).

Adherence to Exercise Training Sessions: The intervention is designed as 12-weeks of exercise training performed 3 times weekly on Monday, Wednesday, and Friday for a total of 36 sessions. However, due to federal holidays, 36 sessions may not be feasible within 12 weeks and so time allowance will be made for 36 consecutive sessions to be performed with 100% adherence. Given that occasional missed exercise sessions will occur (usually due to travel in our experience), up to 3 additional exercise sessions will be offered to allow participants to reach 36 exercise training sessions. This provision minimizes the risk of muscle strain and exercise intolerance by allowing sufficient time to reestablish training progression and is a standard approach in progressive exercise training trials.

3.2.b Randomization

After baseline testing is complete, eligible participants will be randomized 1:1 to VTEL exercise or standard of care control groups. Randomization will occur in blocks of 2-10 participants at each site. An independent statistician will provide an allocation list for each site that will be managed by an individual without access to study data or contact with participants. The size of the block may vary by site and COVID safety practices. Block randomization is routinely used in smaller trials to ensure equal distribution between groups. In this application, it also serves to adjust the cohort size of each exercise group from a minimum of one participant to a maximum of five participants.

3.2.c Delayed Entry Exercise for Control Group

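### Randomisation is stratified by site, but no between-group model names site; in baseline-adjusted ANCOVA the reported standard error is slightly too large if site stays prognostic (low priority)

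*Combined protocol and SAP*

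**What the plan says.** Section 3.2.b (Randomization) allocates 1:1 and states "Randomization will occur in blocks of 2-10 participants at each site". It adds that "An independent statistician will provide an allocation list for each site". Section 3.1 plans 40 participants at each of two sites. The plan does not use the word, but this is randomisation stratified by site. Section 3.2.b also uses the blocks to set the size of each exercise cohort, from "a minimum of one participant to a maximum of five participants".

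Section 2.3.e (Statistical Plan) describes the between-group test for Aims 1 and 2 as "ANCOVA will be used to test for between group difference by time (pre/post exercise". On covariates it says "Baseline performance and demographic and clinical characteristics will be included in models to assess and adjust for known potential confounding factors", without listing them. For Aim 3 the regression carries a "vector of covariates including age, race, smoking status and leukocyte proportions", and then: "We will extend this linear regression model to account for batch/chip effects", with a linear mixed model also covering the longitudinal measures. Site appears in none of these. Dropouts are to be handled by multiple imputation, and the content of the imputation model is not given.

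**The concern.** When allocation is blocked within site, the arms are balanced on site by design. If site also predicts the outcome, that balance makes the treatment estimate more precise. A linear model without site does not credit this: the between-site variance is counted as residual error, the standard error is overstated and the test is conservative. The estimate itself is not biased.

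At stake is a little reported precision, and an analysis that reflects how participants were randomised. The point concerns the linear ANCOVAs: VO₂peak, 2-minute step test, DNAm Age, methylation, and also the plasma cytokines, which section 3.3.b assays locally at each site. No precision claim is made for the logistic and multinomial models of sarcopenia and frailty. There, adding site does not shrink the standard error and it changes the odds ratio being estimated.

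**Working it through.** **Inputs from the documents.** Two sites with 40 each, 80 in total (3.1); 1:1 blocks of 2-10 with a list per site (3.2.b); expected attrition 30% (3.3.a), so 80 × 0.70 = 56 analysed; alpha 0.05, 80% power and pre/post correlations 0.3, 0.5 and 0.7 (2.3.e).

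**Assumptions.** Two-sided tests; independent errors; baseline value in the model (section 2.3.e does not name it for Aim 3); a site gap *d*, in residual SDs after baseline adjustment, for which the documents give no value.

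**The plan's own figures.** None concerns site. The sample-size table uses a paired t-test without a site term. Its DNAm Age row reproduces: the SD of change is √(10.8² + 10² − 2·r·10.8·10) = 12.32, 10.42 and 8.09 for r = 0.3, 0.5 and 0.7. With a change of 6.7 years, a two-sided test needs 29, 21 and 14, as stated. That supports the two-sided assumption but does not bear on site.

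**1. Closed form, site balanced across arms.** A balanced two-level factor has variance 1/4, so omitting it inflates the residual variance by d²/4 (times N/(N−2)). The multiplier for the treatment coefficient is unchanged:

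SE without site / SE with site = √(1 + (d²/4)·N/(N−2)).

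Example, d = 0.5, N = 56: √(1 + 0.0625 × 56/54) = √1.0648 = 1.032.

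**2. Power.** Simulation with 40,000 replicates, baseline in the model, balance within site, and the effect set for 80% power (0.763 residual SD at N = 56, 0.635 at N = 80):

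| Residual site gap *d* | SE ratio, N = 56 / 80 | Power without vs with site, N = 56 | Power without vs with site, N = 80 |
|---|---|---|---|
| 0 | 1.000 / 1.000 | 79.6 vs 79.6 | 79.0 vs 79.0 |
| 0.2 | 1.005 / 1.005 | 79.3 vs 79.4 | 79.4 vs 79.7 |
| 0.3 | 1.012 / 1.011 | 78.5 vs 79.1 | 78.7 vs 79.3 |
| 0.5 | 1.032 / 1.032 | 77.5 vs 79.1 | 77.7 vs 79.5 |

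At d = 0.5 the true SD of the estimate does not move: 0.2701 without and 0.2700 with site (N = 56), 0.2243 and 0.2242 (N = 80). Only the mean reported SE moves: 0.2773 vs 0.2687 and 0.2315 vs 0.2244.

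**3. Permuted blocks of 2-10.** A separate simulation (8,000 replicates, N = 80, pre/post correlation 0.5) gave SE ratios of 1.005 and 1.031 at d = 0.2 and 0.5. Type I error without site was about 0.044 at d = 0.5. With 30% random dropout the ratio at d = 0.5 was 1.028. Power at an effect of 0.65 residual SD, where it is only about 65%, was then 62.9% without and 65.3% with site.

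**4. Stable raw offset.** If the sites differ by 0.5 SD at both visits, baseline absorbs most of it. With v = 1.0625, the ratio is √{[v − (r + 0.0625)²/v]/(1 − r²)} = 1.016, 1.010 and 1.005 for r = 0.3, 0.5 and 0.7. The power loss is 1 point or less.

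**5. Cost if site is not prognostic.** With 30% random dropout the ratio is 0.996-0.997, so adding site raises the SE by 0.3-0.4%.

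**6. Pre/post group-by-time model.** In a random-intercept fit, a site main effect leaves the group-by-time SE unchanged (ratios 1.000-1.001 in all settings). Site-by-time matters only if site shifts the change itself. For a shift of D SD, put d = D/√(2(1−r)) into the formula in step 1. D = 0.3 gives 1.008, 1.012 and 1.019; D = 0.5 gives 1.023, 1.032 and 1.053 for r = 0.3, 0.5 and 0.7.

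**The case against.** **No error is shown and the size is assumed.** True: there is no bias, true precision barely changes, and the open covariate wording would permit site. The documents give no site gap. Several features would limit one: baseline adjustment, batch/chip adjustment in Aim 3, video supervision of functional testing from Salem, pre/post samples in one assay, and a single methylation laboratory. Against this, treadmill tests and cytokine assays are done locally, so a gap is possible. The word slightly also depends on the range considered. At gaps of 0.8 and 1.0 SD with all 80 followed, the SE is about 8% and 12% too large and power falls by about 5 to 8 points. Nothing in the documents supports gaps of that size.

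**The test may be a group-by-time contrast.** The wording allows it, and step 6 shows that a site main effect is then irrelevant. This changes which term to add, not the need to state it.

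**Clustering in exercise cohorts could cancel the gain.** This is the strongest objection. With cohorts of five, an assumed intraclass correlation of 0.03 and a 0.5 SD site gap, the reported SE divided by the true one is about 1.00 to 1.01 without site and 0.97 with it. At 0.01 and the same gap it is 1.02 and 0.99. A modest cohort effect can therefore remove the benefit, and adding site alone can leave the SE too small. That stands, and it limits the claim to the site term under independent errors. It is a reason to consider the cohorts as well, not to leave site out. A site term also reflects only the outer layer of an allocation made in blocks within site.

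**The planned imputation was not modelled.** Also true: the dropout figures are complete-case. Including site in the imputation model rests on the principle that it should contain the variables in the analysis model, not on a calculation.

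**Conclusion.** The concern holds, at low priority. Site is a stratification factor and no between-group model names it. In baseline-adjusted ANCOVA with independent errors, omission makes the reported SE about 0.5% to 3.2% too large for residual gaps of 0.2 to 0.5 SD, and costs under 2 points from 80% power. At zero gap there is no loss. The figures are for a single two-sided 5% test; Aim 3's Bonferroni threshold was not modelled. The statement that true variability is unaffected is close rather than exact: at a raw offset of 1.0 SD and r = 0.3 the true SD is 0.2157 without and 0.2134 with site (N = 80), and 0.2657 and 0.2607 with 30% dropout. No net direction is claimed once exercise cohorts are considered.

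**What to change.** State in section 2.3.e that site (Atlanta or Baltimore) is a fixed effect alongside the baseline value in every between-group ANCOVA, and that site is included in the multiple-imputation model. If the between-group test is instead a pre/post mixed or repeated-measures model with a group-by-time contrast, include site-by-time.

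The cost is one sentence and one degree of freedom per ANCOVA, or normally two where site-by-time is added with its main effect. Site is already recorded for every participant.

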3.2 Coordinating Center at the Salem VAMC (Research Activities Conducted at SVAMC)

3.2.a Exercise Intervention: VTEL Exercise Training

Exercise Training Description

The exercise physiologist located at the SVAMC will be responsible for conduct of all exercise training under the supervision of the PI. Exercise training will be delivered by VTEL broadcast from the Salem VAMC to participants at the Atlanta VAMC and Baltimore VAMC. In the event that the Salem EP is not available to deliver the training, the exercise training can be delivered by another experienced EP through a telehealth platform. Research staff at the Atlanta and Baltimore VAMCs will be in the room with the participant to help with heart rate monitors and portable exercise equipment, and in the event of an emergency. Rooms will be equipped with steps, hand and ankle weights, dumbbells, chairs, and bands. No stationary exercise equipment will be used in either aerobic (AEX) or resistance training (RT). The intervention consists of high-intensity circuit exercise training performed 3 times weekly for 12 weeks in a group setting. Circuit training is an exercise modality consisting of a series of exercises at different stations.

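### Exercisers train in small site classes and controls do not, but the between-arm models treat everyone as independent and carry no class or site term; the likely error is small and cheap to remove

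*Combined protocol and SAP*

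**What the plan says.** Randomization is individual: section 3.2.b states that "eligible participants will be randomized 1:1 to VTEL exercise or standard of care control groups", and "Randomization will occur in blocks of 2-10 participants at each site". The same section adds that the blocks have a second purpose: "it also serves to adjust the cohort size of each exercise group from a minimum of one participant to a maximum of five participants". Section 3.1 gives the arm sizes: "Eligible participants will be randomized to exercise training (N=40) or control (N=40) groups".

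The exercise programme is "performed 3 times weekly in a supervised group setting" (section 3.1). On delivery, section 3.2.a says: "Exercise training will be delivered by VTEL broadcast from the Salem VAMC to participants at the Atlanta VAMC and Baltimore VAMC". It does not say whether the two sites attend the same session. For the comparison arm, section 3.1 says: "Participants in the Control Group will be instructed to maintain their baseline sedentary lifestyle". The controls' later delayed-entry results are kept out of the randomized analyses, so the group sessions in that phase do not cluster the control arm.

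Section 2.3.e plans ANOVA for VO2peak, the 2-minute step test and DNAm Age, logistic or multinomial models for sarcopenia and frailty, and ANCOVA for the between-group difference over time. The named covariates are baseline performance and demographic and clinical characteristics. The only mixed model is the Aim 3 extension for batch/chip effects and repeated measures. No class, cohort, block or site term appears, and there is no cluster-robust variance, ICC or design effect.

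**The concern.** People who train together three times a week for 12 weeks may come to resemble one another in their response. The protocol itself gives one reason: section 3.2.c says peer support has been seen in the VTEL sessions, and section 3.3.b plans to relate social support to attendance and retention. If class members do respond alike, 40 exercisers carry less information than 40 independent people, while the 40 controls carry their full weight. A model that assumes independence then gives a standard error that is too small, confidence intervals that are too narrow and a type I error above 5% in the between-arm comparisons. Because the blocks deliberately set class size, the structure is built into the design and can be planned for.

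**Working it through.** **Inputs from the documents.** 40 per arm (3.1). Blocks of 2 to 10 per site at 1:1 (3.2.b), so 2/2 = 1 to 10/2 = 5 exercisers per block, which reproduces the stated cohort range. Table 5: 3 completers per site in a typical quarter, both arms together. Expected attrition 30% (3.3.a).

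**Input not in the documents.** The within-class ICC. I assume 0.05 and 0.10.

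**The plan's own figure.** The largest requirement in the Aim 1/Aim 2 sample-size table is DNAm Age, with 29 / 21 / 14 at pre/post correlation 0.3 / 0.5 / 0.7. At 0.3, the SD of change = √(10.8² + 10² − 2×0.3×10.8×10) = 12.32 and the effect is (68.7 − 62)/12.32 = 0.54. A two-sided paired t-test at 80% power needs 29. The other two values also reproduce. This is a one-group calculation for independent participants, with no design effect.

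**Likely class size.** A class lasts about one quarter. Three completers per site per quarter at 1:1 gives 1.5 exercisers, or 1.5/0.70 = 2.1 as randomized. If the two sites did share a session, the class would hold 3 completers, or 3/0.70 = 4.3 as randomized. Batched enrolment could make some classes larger.

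**Effect on the test.** With class size m:
- exercise-arm design effect: DE = 1 + (m − 1)×ICC; control arm: 1
- variance inflation of the arm difference (equal arms): V = (DE + 1)/2
- true SE / naive SE = √V
- true type I error = 2×[1 − Φ(1.96/√V)]

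Example, m = 5 and ICC = 0.10: DE = 1.40, V = 1.20, √V = 1.095, type I error = 2×[1 − Φ(1.79)] = 7.4%.

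| Class size | SE ratio, ICC 0.05 / 0.10 | Type I error, ICC 0.05 / 0.10 |
|---|---|---|
| 1 | 1.000 / 1.000 | 5.0% / 5.0% |
| 2 | 1.012 / 1.025 | 5.3% / 5.6% |
| 3 | 1.025 / 1.049 | 5.6% / 6.2% |
| 4 | 1.037 / 1.072 | 5.9% / 6.8% |
| 5 (stated maximum) | 1.049 / 1.095 | 6.2% / 7.4% |
| 10 (extreme bound) | 1.107 / 1.204 | 7.7% / 10.4% |

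Simulation of a naive t-test (40 per arm, 40,000 runs) agrees: 5.2% / 5.6% for classes of 2 and 6.3% / 7.4% for classes of 5. An assumed mix of class sizes from 1 to 5 gives 6.0% / 6.5%.

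**The opposing omission.** Both arms are drawn from the same site blocks, so a site or calendar effect is shared by the arms and cancels in their difference. A model without that factor leaves it in the residual, and the naive SE is then too large. The same simulation was run with an assumed shared block variance of 0.05 / 0.10 of the total:
- classes of 2, ICC 0.05: 4.7% / 4.2%
- classes of 5, ICC 0.05: 5.6% / 5.1%
- classes of 5, ICC 0.10: 6.9% / 6.5%

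**The case against.** The case for leaving the plan alone has four parts.

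1. **Class size.** Five is a cap, and Table 5 points to about two exercisers per site. This stands, and it holds the likely inflation to a fraction of a percentage point. A reader might infer from the two-site broadcast that classes reach ten and type I error exceeds 10%. The documents do not say that the sites share sessions, and ten would need both sites at their maximum at once.

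2. **Mechanism.** One Salem exercise physiologist normally leads all training, so that person's style shifts the arm mean and adds little variation between classes. Section 3.2.a sets heart-rate limits for each participant and takes strength work to fatigue. This also stands: shared instructor pace or class progression is weakly supported. Peer support is what remains, with no evidence of how strongly it correlates VO2peak, DNAm Age or cytokine changes.

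3. **Direction.** A reader might infer that every between-arm test is anticonservative. The documents do not establish this. The omitted site/block factor can offset the clustering at small class sizes. Moreover, if exercise affected nobody, classes could not create correlation through the intervention; the inflation belongs to a null in which class effects exist but average to zero. Two omissions that may partly cancel are still no basis for a standard error, and interval coverage suffers whenever class effects exist.

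4. **Remedy.** With many classes of 1 or 2, the class variance is poorly separated from the residual, and an estimate that cannot go below zero tends to be too high. Mixed or class-robust models for sparse sarcopenia and frailty categories may be unstable. This stands and limits the remedy for the categorical outcomes.

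**Conclusion.** The point holds as a gap in the analysis plan of small to moderate size. The exercise arm is nested in classes, the control arm is not, and no planned between-arm model reflects either the classes or the site blocks. On the clustering alone, type I error would be about 5.3% to 5.6% at the class size that accrual suggests and 6.2% to 7.4% at the stated maximum. These figures rest on assumed ICCs of 0.05 and 0.10, equal arms, equal total variance and no shared block effect. With a shared block effect the net error may be nil or reversed for classes of 2.

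A reader might also infer that the stated sample sizes are wrong because of clustering. They are not: they are one-group paired calculations. Whether that basis suits a between-arm test is a separate question.

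**What to change.** - Define the training class as a site cohort or, if sessions are shared, a joint broadcast group, and record its ID for every exercise session. The per-session training logs in section 3.2.a may allow past classes to be reconstructed, but recording the ID prospectively is safer.
- For continuous outcomes, fit the between-arm ANCOVA with site as a fixed effect and a random class intercept in the exercise arm only, each control being a cluster of one. Use Satterthwaite or Kenward-Roger degrees of freedom and report the estimated ICC.
- For sarcopenia and frailty, keep the planned models and add class-robust variance as a sensitivity analysis only.

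The site term removes the site part of the effect shared by both arms. Any calendar part stays in the residual and errs towards caution.

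The cost is SAP wording and one ID variable, with no new visits or procedures. Intervals will be slightly wider. In simulation, a class-level analysis brought type I error back to about 5% and cost 0.5 to 3 percentage points of power when the true ICC was zero. If the class variance is estimated at zero, the result is essentially that of the same ANCOVA without the class term.
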